The primary outcome measure will be the incidence and rate of “relapse,” defined as a blood pressure level that has risen to the baseline value (blood pressure value of the participant at the time of enrollment) for three consecutive days.

If, over the course of 15 days there is evidence of a gradual recurrence of symptoms, the experimental period can be extended. If there is no evidence of impending relapses, there are two options: (a) we can reduce the partial reinforcement schedule from 25% to 15%, for example, and adjust the dose of in the Dose Control Groups accordingly; or (b) proceed to a study of extinction effects (Experiment 2).

Timeline estimate. We propose a start-up period of 6 mo. (formulation of Consent Form, IRB approval of protocol, preparation of study personnel, data management procedures, preparation and placing of advertisements for study subjects, etc). Including an instructional session and testing of blood pressure measurements from the monitors provided to patients, patients enrolled in the study could be engaged for as many as 50-60 days. We calculate being able to process 40 patients/year. A final 6 mo. would be devoted to data processing and manuscript preparation and, thus, a total project period of 4 years.

Experiment 2. *Effects of CS exposure on the persistence of drug effects following the withdrawal of drug and the effects of partial schedules of pharmacotherapeutic reinforcement on resistance to extinction.*

Based on the time available and the outcome of Experiment 1, we may be able to gather additional preliminary data on the extinction of conditioned pharmacotherapeutic effects, adding evidence that results obtained in Experiment 1 are, in fact, the results of conditioning. We expect that patients in Dose Control Group-II from Experiment 1 will relapse within 2-3 days of the treatment imposed during the experimental period. A large percentage of Dose Control Group-I patients are also expected to relapse under a reduced dose of active drug during the experimental period. However, we expect that a significant percentage of patients in the Partial Reinforcement Group (as well as the Standard Therapy Group) would be available for further study of extinction effects.

The literature suggests and our own data (Suchman & Ader, 1992) indicate that the persistence of the therapeutic effects of at least some drugs after drug treatments have ended cannot be attributed solely to the residual effects of the drug. We infer that there is a component of learning in the repeated pairing of distinctive sensory cues and the therapeutic effects of drugs. Therefore, *it is predicted that, when active drug treatment is discontinued, reexposure to conditioned stimuli previously associated with effective drug treatment will extend the effects of the pharmacotherapy beyond that resulting from the residual effects of the drug.* That is, in hypertensive patients being treated with, the ameliorative effects of the pharmacotherapy will persist for a longer period of time (relapse will be delayed) in those patients who continue to be exposed to the conditioned stimulus (placebo “medication”) than in patients who receive no “medication” following the withdrawal of active drug.

Performance during a period of extinction—when subjects are reexposed to a CS that is *not* followed (reinforced) by the UCS (active drug)—constitutes a particularly sensitive measure of the strength of learned responses. The “partial reinforcement effect” in conditioning refers to the observations that responses acquired under partial schedules of reinforcement are more resistant to extinction than responses acquired under continuous reinforcement. Therefore, *it is predicted that when active drug is withdrawn and replaced by CSs alone, resistance to extinction will be greater (i.e., rate of relapse will be less) among patients treated under a partial schedule of reinforcement than patients treated with the same*

amount of drug administered under a continuous schedule of reinforcement. If this turns out to be the case, this strategy might profitably be applied in attempting to wean patients from certain drugs.

A comparison of groups that are or are not reexposed to the CS following the discontinuation of active drug therapy and an assessment of extinction effects as a function of reinforcement schedule are separate issues, but they could (should) be addressed in a single experiment.

If, as anticipated, there are a sufficient number of patients from Experiment 1 who show no evidence of relapse within the 15-day experimental period, we can proceed to Experiment 2. The remaining patients from the Standard Therapy and Partial Reinforcement Groups (and, perhaps, the Dose Control Group-1) would be divided into two subgroups. For one subgroup, all medication would be discontinued for a period of 2-4 wk; for the other subgroup, active drug would be discontinued but the patients would continue to receive the distinctive capsules containing inert substance. It is predicted that: (a) patients reexposed to the CS will be less likely to relapse or show a slower rate of relapse than patients in groups that are not reexposed to the CS; and (b) patients in the Partial Reinforcement Group will be more resistant to extinction (slower to relapse) than patients remaining from Dose Control Group-1 who were treated with the same cumulative amount of drug and may even be indistinguishable from the Standard Therapy Group that had received three times more drug. An alternative strategy, of course, would be to enlist a new population.

c) Statistical Analysis: Data analyses are described separately for each of the specific hypotheses. All statistical tests will be two-sided with $p \leq .05$. The principal analyses focus on the difference over 2-weeks between PR and two dose control groups (DC-1 and DC-2) in Experiment 1. The main independent variable is time to relapse as well as symptom reduction (blood pressure). These two outcomes will also be examined in Experiment 2 to see if they differ between the two groups (placebo and no-treatment groups). Because power for the comparisons in the second experiment may be undercut by high relapse rates in the first experiment, this second set of analyses is exploratory.

The Cox proportional regression model will be used to examine the time to relapse outcome, while mixed-effects (MM) model will be used to compare differences in symptom reductions over time across the treatment groups. The MM approach employed for longitudinal data analysis provides valid inference under the missing at random assumption (MAR), provided that the parametric distribution assumptions are met. The MAR model is quite general, accommodating almost all missing data mechanism that may arise in practical studies (37,38). However, in the presence of missing data, estimates in both cases may be biased if the data fails to follow the assumed statistical distributions, even with the use of the sandwich variance estimates (39). In cases where distribution assumptions are seriously violated, for example, if discrepancies between the MM and WGEE for fixed-effects show very different results, we will use clustered bootstrap methods for inference (40).

Experiment 1

AIM 1: a) PR will be more effective than DC-1 and DC-2 in reducing relapse rates. PR will have similar effectiveness to ST in reducing relapse rates.

Survival analysis will be conducted using Cox proportional hazards model. We will include dummy variables for the four treatment groups in addition to the covariates found to significantly differentiate the groups at baseline. Appropriate linear contrasts will be constructed to compare PR vs. each of the dose control groups, if a significant group difference is found.

Note that to formally confirm the equivalence between PR and ST, we must use non-inferiority tests. However, since the acceptable margin of tolerable difference is difficult to define due to the lack of insufficient literature on this topic, we will not conduct such a formal analysis. The effect size will provide similar indications of treatment difference.

b) PR will have higher (similar) symptom reductions than DC-1 and DC-2 (ST).

Longitudinal methods will be applied to compare the outcomes of pruritus and biologic measures across the four groups as well as the appropriate pairwise comparisons. We will dummy code the treatment conditions, include time and time by treatment interaction in addition to the covariates found to differentiate

the four groups at baseline. The hypothesis will be supported if a significant time by treatment interaction is found. Appropriate linear contrasts will be performed to compare PR vs. DC-1, DC-2 and ST.

Experiment 2

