b) Number of Subjects: 121. Sample size and Power Analysis: The proposed study will recruit 37 subjects for each of the ST, PR and DC1 treatment conditions, and 10 subjects for the CD2 group. The study has 93% power to detect a 50% difference in relapse rate between group 2 and group 3 over the 2-week assessment period, even account for 10% dropout rate based on a two-sided $\alpha = 0.05$ using the method of Lakatos, E. (35). We selected a 50% relapse rate difference for the power calculation based on our prior experience. For the primary continuous symptom measure blood pressure, we have 80% power to detect about a medium effect size 0.56 based on a longitudinal study design with 7 assessment points, a conservative estimate of within-subject correlation 0.5, and a two-sided type I $\alpha=0.05$ using the method of Tu et al. (36). Note that although blood pressure is assessed twice daily in Experiment 1, we conservatively set the number of assessments at 7 to improve the robustness of the power estimates. Thus, the proposed sample size not only has sufficient power to detect a clinically meaningful difference in relapse rates, but also to find meaningful change patterns for blood pressure over the treatment course.

c) Sex of subjects: The male to female ratio will follow the distribution of hypertension in the Rochester area community. Pregnant or nursing females will be excluded due to the nature of the intervention (carvedilol is Category C). Females of child bearing potential will be required to use 2 birth control methods during the study in order to participate.

d) Age of Subjects: 18 to 80 years of age. Carvedilol is not intended for use in children.

e) Racial and Ethnic Origin: No restrictions. It will follow the distribution of patients seen in the Rochester area.

f) Vulnerable Subjects: None will be enrolled.

III. METHODS AND PROCEDURES

a) **Study Design.** Randomized, single blind.

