Medication. Hypertensive patients will be treated with distinctively colored, *odored and flavored* gelatine capsules (Capsuline, Inc, Pompano Beach, FL) containing 12.5 mg (generic version, available from the Strong Memorial Hospital Research Pharmacy). The “placebo” will be a capsule containing 12.5 mg of an inert substance with the same characteristics as the active drug capsules. Capsules will be packaged in a blister strip of single application packets by the Investigational Drug Studies program in the Strong Memorial Hospital Research Pharmacy. Preparation of the sequence of medication would be done from coded patient numbers and would depend upon the schedule of reinforcement that was being used. For example, if one were imposing a 25% reinforcement schedule (only one fourth of the packets of capsules containing active drug), a random sequence would be constituted with the proviso that the patient would receive no more than two doses of consecutive placebo capsules. Randomization will be performed by the research pharmacy in blocks of eight. Allocation concealment will be guaranteed, since only the research pharmacist will be aware of group distribution and all other members of the research team will be blinded. He will provide the research nurse with the pre-labeled packages.

Length of study: 8 weeks for those subjects that complete the full set of procedures. For those subjects who relapse early, or whose blood pressure does not remit (10-point decrease for a period of 5 days) prior to the Exp 1 phase, the minimal period in the study is 3 weeks.

Exp 1: Baseline Period: 2 weeks after a screening physical examination that will be performed within one week of admission. ; Experimental Phase: 2 weeks (or less for subjects' whose mild hypertension relapses). Therefore, maximal possible period receiving carvedilol: 4 weeks.

Exp 2: 4 weeks. In this experiment subjects either receive placebo or no treatment. We expect the latter group to relapse after a few days. Those receiving placebo are hypothesized to relapse later, and we are assuming that will relapse before 4 weeks on placebo. However, if we find that there are subjects that after 4 weeks have not relapsed, we plan to continue the administration of the placebo until they relapse (beyond the 4 weeks). Because we believe that this will occur rarely, for practical reasons we will state in the consent form that this period may last “up to 4 weeks”.

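### The 80% power stated for blood pressure makes no allowance for series that end at relapse; on the plan's own 7-assessment basis the planned time-by-treatment test has roughly 36–68% power

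*Combined protocol and SAP*

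**What the plan says.** Section II.b (Number of Subjects) states that "we have 80% power to detect about a medium effect size 0.56 based on a longitudinal study design with 7 assessment points", with "a conservative estimate of within-subject correlation 0.5" and two-sided alpha 0.05. It adds that 7 is a cautious choice, because pressure is measured twice daily. The trial "will recruit 37 subjects for each of the ST, PR and DC1 treatment conditions, and 10 subjects for the CD2 group". The phrase "even account for 10% dropout rate" belongs to the preceding sentence, on relapse power, which claims 93% for a 50% difference in relapse rate. No absolute rates are given.

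Section III.a (Length of study, Exp 1) gives "Experimental Phase: 2 weeks (or less for" subjects who relapse. Relapse is a pressure back at the enrolment value for three consecutive days (Experiment 1). The introduction to Experiment 2 says: "A large percentage of Dose Control Group-I patients are also expected to relapse under a reduced dose of active drug during the experimental period".

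For Aim 1(b), section III.c will "include time and time by treatment interaction" in a longitudinal model and treats a significant interaction as support for the hypothesis. Aim 1(b) names pruritus as an outcome; I read it as blood pressure, because the opening of III.c defines symptom reduction that way. The plan does not say whether readings continue after relapse, or whether time is linear or categorical.

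**The concern.** The power sentence and the conduct of the trial describe different data sets. The power sentence fits complete series. The conduct sections lead one to expect short series in the main comparator arm, because its patients are expected to relapse and relapse ends the phase. A slope or interaction test depends on the length of time each patient is observed, so early exit costs it more than it would cost a comparison of averages.

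Blood pressure is the plan's primary continuous measure and part of its principal analyses, and II.b concludes that the sample is adequate for it. If that is not so, a null interaction could be misread as evidence against the conditioning hypothesis. Exit also comes just as pressure has climbed back to the enrolment value, so a wrongly shaped time trend could distort the estimated difference.

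**Working it through.** **Inputs from the documents.** 37 per arm for PR and DC-1; 10% dropout, giving 37 × 0.9 = 33.3; 7 assessments; correlation 0.5; effect 0.56; two-sided alpha 0.05; 15-day period.

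**Assumptions.** Compound symmetry, equally spaced assessments, the effect taken as the end-of-period difference in SD units, dropout applied to blood pressure as well, and no readings after relapse.

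**1. The plan's figure.** With time scaled 0 to 1 in steps of 1/6, the sum of squared deviations is 28/36. Slope variance per patient is (1 − 0.5) × 36/28 = 0.643. The SE of the difference is √(2 × 0.643/33.3) = 0.1965. Power is Φ(0.56/0.1965 − 1.96) = Φ(0.89) = 81%. The detectable effect at 80% power is 2.80 × 0.1965 = 0.55. With 37 per arm, power is 85%. An end-point ANCOVA with 37 per arm also comes close (79.4%), but it does not use 7 points.

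**2. Relapse rates.** None are stated. I read the 50% difference as a halving and use a two-proportion formula with 33.3 per arm. For 40% versus 80%:

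(0.40 − 1.96 × √(2 × 0.6 × 0.4/33.3)) / √((0.24 + 0.16)/33.3) = (0.40 − 0.235)/0.110 = 1.50, so power is 93%.

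The same formula gives 56% at 25/50 and 70% at 30/60. The plan used a log-rank method, so the fit of 40/80 to the stated 93% is approximate and inferred.

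**3. Exit at relapse, 7 points.** With relapse probability p by day 15, the constant hazard is −ln(1 − p)/15. A patient contributes the k assessments up to relapse. Information per arm is n × Σ P(k) X′V⁻¹X over those k points, and the slope variance is read from its inverse.

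| Relapse PR/DC-1 | Mean assessments PR, DC-1 | SE | Power at 0.56 | Detectable effect |
|---|---|---|---|---|
| none | 7, 7 | 0.197 | 81% | 0.55 |
| 25/50% | 6.1, 5.1 | 0.235 | 67% | 0.66 |
| 30/60% | 5.9, 4.6 | 0.248 | 62% | 0.69 |
| 40/80% | 5.5, 3.6 | 0.293 | 48% | 0.82 |
| 45/90% | 5.3, 2.9 | 0.348 | 36% | 0.97 |

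If relapse cannot occur before day 3, the four truncated figures become 68%, 63%, 50% and 40%. With 37 per arm (relapse from day 0) they are 71%, 66%, 52% and 40%. Timing matters too: at 40/80 with 33 per arm, power is 41% if relapses fall on days 3–7 and 60% if they fall on days 7–15. The most favourable case tried (25/50, relapse on days 7–15, 37 per arm) gives 75%.

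**4. All twice-daily readings.** 15 days × 2 = 30 occasions, 33.3 per arm, relapse at 25/50, 30/60, 40/80 and 45/90:
- Pure compound symmetry: 99%, 99%, 94%, 84%.
- Correlation 0.5 + 0.5 × 0.5^lag between occasions: 81%, 77%, 63%, 50%.
- Correlation 0.5 + 0.5 × 0.7^lag: 65%, 61%, 48%, 38%.
- Compound symmetry plus random-slope variance 0.25 to 0.5, at 40/80: 68% to 52%. Complete 7-point power is then itself only 68% to 57%.

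**5. Bias if time is linear.** Simulation with 20,000 patients per arm, true end difference 0.56, series cut after three consecutive days above a threshold set so that 50% or 80% of DC-1 relapse:

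| True shape | Linear fit, complete series | Linear fit, cut series |
|---|---|---|
| Linear rise | 0.55–0.57 | 0.53–0.57 |
| Rise, plateau from day 7 | 0.52–0.55 | 0.56–0.96 |
| Faster plateau | 0.32–0.41 | 0.40–0.82 |
| Convex (late) rise | 0.55–0.58 | 0.43–0.52 |

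**The case against.** The best reply is that 7 was deliberately set well below the 30 planned occasions, so removing readings from 7 ignores the plan's own margin: an early relapser may still supply 7 readings. This is right as far as it goes, and under pure compound symmetry the margin is ample. But those readings cover a shorter span. Half-day readings in one patient are also unlikely to be free of serial correlation, and step 4 shows how quickly the margin then disappears. The plan offers 7 as its robust basis, so its 80% is fairly judged on 7.

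Second, no relapse rates are stated, so no single corrected figure exists. That stands. A reader might infer that the test has half its stated power. The documents do not support this: even at 40/80 the ratio is 48/81 = 59%, and milder or later relapse gives more.

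Third, relapse is defined on observed pressure, so exit at relapse is close to missing at random, which III.c assumes. That also stands. A reader might infer that the model must favour PR whenever relapse rates differ. It need not: with the right mean shape there is essentially no bias, and with a late rise the bias runs against PR. A separate set of simulations gave 1.4- to 2.0-fold overstatement, but every scenario in it had pressure levelling off. In its worked example (true difference 5.60 mmHg, cut-data fit 9.89), the complete-data fit was already 6.71, so part of the error came from the straight line itself. Linear time is nowhere specified, and categorical time already fits the text.

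Fourth, a time-averaged comparison would lose little (82–88% at the same rates). However, III.c names the interaction as the test. The comparison of mixed-model and weighted GEE results in III.c, with its bootstrap fallback, addresses distributional violations, not the mean shape after exit.

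Finally, relapse is the primary outcome and its power is not affected by this point.

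**Conclusion.** The point holds in a limited form. The stated 80% matches a complete-data calculation and leaves out a loss of data that the protocol itself anticipates. On the 7-point basis, power for the interaction test is roughly 36–68% with 33.3 per arm. At the one pair of rates that fits the stated 93% relapse power, it is about 48–50%, with a detectable effect of about 0.8 in place of 0.56. These figures rest on assumed relapse rates and timing, compound symmetry, linear time, and the reading that blood pressure collection stops when the phase ends. The last is the natural inference, but it is not stated.

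The bias is conditional. It arises only if time is fitted with the wrong shape: upward in most rise-then-plateau cases, downward for a convex rise, and negligible for a linear one. The documents give no trajectory from which to tell which applies.

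**What to change.** 1. **Section II.b.** State the relapse rates assumed for PR and DC-1, and restate the blood pressure power, or the detectable effect, with exit at relapse. Give the covariance assumed, and if credit is taken for more than 7 readings, allow for serial correlation and random slopes. Cost: wording and a less favourable figure.

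2. **Data collection.** Ask all randomised patients to keep recording home pressure to day 15 after relapse, flag readings taken after any treatment change, and analyse with and without the flagged readings. Patients already hold the monitors. Cost: a few more days of readings for relapsers, some of which may reflect resumed treatment.

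3. **Aim 1(b).** Specify time as categorical (day or week), and name the PR versus DC-1 contrast to which the restated power refers. Cost: more parameters, and less power than a correctly shaped linear trend would have.

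Carrying the relapse level forward over the remaining days should be at most a sensitivity analysis. It treats unobserved values as known and builds in a plateau.
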